Comparison of the Efficacy of Single and Double Puncture Arthrocentesis in Treatment of Temporomandibular Joint Disc Displacement Without Reduction

Date: 20/03/2020

This document contains study design and statistical analysis plan of the study entitled "Comparison of the Efficacy of Single and Double Puncture Arthrocentesis in Treatment of Temporomandibular Joint Disc Displacement Without Reduction".

Study Design:

This is a two-armed, randomized, parallel interventional clinical study enrolling 36 patients with temporomandibular joint disc displacement without reduction (DDwoR).

*Eligibility:**Inclusion Criteria:*

- Clinical diagnosis of Temporomandibular joint (TMJ) disc displacement without reduction.
- Restricted mouth opening

Exclusion criteria:

- History of systemic disease effecting TMJ.
- History of previous TMJ surgery

Patients were grouped according to the treatment they received: Single Puncture Arthrocentesis as group SPA, Double Puncture Arthrocentesis as DPA.

Double puncture arthrocentesis technique:

Posterior puncture method was used as described by Alkan and Etoz for DPA. A straight line was drawn with a marker pen along the skin from the middle portion of the auricular tragus to the lateral chantus. The first puncture point was marked 10 mm anterior and 2 mm inferior to the tragus and the second 7 mm anterior and 2 mm inferior to the tragus. After local anesthesia, upper joint cavity was irrigated with 200 mL of Lactated Ringer's (RL) solution by inserting two 21- gauge needle. At the end of the procedure, after withdrawn of one of the needles, 1 mL of sodium hyaluronate (SH) was injected into the upper TMJ compartment through the other needle.

Single Puncture Arthrocentesis Technique:

SPA was performed with one needle (SPA Type-1 according to Senturk and Cambazoglu). The first reference point in DPA was used as the needle entry point fort he SPA. With this technique, the inflow and outflow of solution were provided through the same cannula and lumen of one 21-gauge needle as described by Guarda-Nardini et al. The joint was irrigated with 200 mL of RL solution under high pressure. At the end of the procedure 1 mL of SH was injected through

the needle

Outcome measures:

1. The Rate of Pain on Function (PoF) assessed by Numerical pain Scale (NRS)

Patients rated their pain on function (pain during chewing or speaking etc.) on a Numeric Rating Scale (NRS) (0–10 where 0 is no pain and 10 is the worst pain imaginable).

Patients were evaluated at preoperatively and postoperatively 1st week, 1st month, 3rd month, 6th month.

2. The measurement of pain-free maximum mouth opening (MMO) in millimeters:

Pain-free MMO was measured as the distance between the incisal edges of the upper and lower incisors by a caliper while patient's mouth is open as possible without any assistance and without pain in masseter muscle. Three measurements were performed, and their average is recorded. Patients were evaluated at preoperatively and postoperatively 1st week, 1st month, 3rd month, 6th month.

3. The rate of pain at rest (PaR) assessed by Numerical pain Scale (NRS)

Patients rated their pain level at rest on a Numerical pain Scale (NRS)(0–10 where 0 is no pain and 10 is the worst pain imaginable). Patients were evaluated at preoperatively and postoperatively 1st week, 1st month, 3rd month, 6th month.

4. Measurement of Duration of the Procedure in Minutes.

Total time for arthrocentesis was noted at the end of the procedure.

Patients were evaluated at the end of the procedure

5. Measurement of the easiness of the procedure to the operator by using Visual Analog Scale (VAS):

The operator rated the degree of easiness of the procedure on a VAS as 0-very easy 10-very difficult to perform at the end of the procedure

6. The rate of treatment tolerability assessed by 5-point Likert-type scale:

The degree to which overt adverse effects and post operative complications (pain, feeling of pressure in TMJ area and disturbing sound) can be tolerated by the patient. Patients were asked to rate the tolerability on a 5 point scale as 0- lowest, 4-highest at operation day, 1st week, end of follow up period (6th month)

7. The rate of chewing efficiency by using Visual Analog Scale (VAS):

Patients rated the chewing efficiency on a VAS as 0-can only eat semi-liquid foods, 10-eat any solid-food. Patients were evaluated at preoperatively and postoperatively 1st week, 1st month, 3rd month, 6th month.

8. Rate of perceived effectiveness of the treatment by using 5-point Likert-type scale:

Patients rated the subjective treatment effectiveness on a 5-point scale as 0- lowest, 4 highest values at the end of the follow up period (6th month).

9. Measurement of Lateral Movement of the mandible towards the affected Temporomandibular joint (TMJ) in millimeters

Lateral Movement of the mandible towards the affected Temporomandibular joint (LT) was measured as the distance between the midlines of the upper and lower incisors by a caliper while patient's mandible was shifted towards the affected TMJ. Three measurements were performed, and their average is recorded. Patients were evaluated at preoperatively and postoperatively 1st week, 1st month, 3rd month, 6th month.

10. Measurement of Lateral Movement of the mandible away from the affected Temporomandibular joint (TMJ) in millimeters

Lateral Movement of the mandible away from the affected Temporomandibular joint (LA) was measured as the distance between the midlines of the upper and lower incisors by a caliper while patient's mandible was shifted away from the affected TMJ. Three measurements were performed, and their average is recorded. Patients were evaluated at preoperatively and postoperatively 1st week, 1st month, 3rd month, 6th month.

11. Measurement of protrusive movement of the mandible in millimeters:

Protrusive movement of the mandible was measured as the distance in horizontal direction between the incisal edges of upper and lower incisors by a caliper when mandible moves forward. Patients were evaluated at preoperatively and postoperatively 1st week, 1st month, 3rd month, 6th month.

Statistical Analysis:

IBM SPSS 22 was used to analyze the data (IBM SPSS Statistics for Windows, Version 22.0. Armonk, NY: IBM Corp.). Descriptive statistics of the variables were presented as mean \pm standard deviation in statistical analysis. Normality of distribution for continuous variables was evaluated using the Kolmogorov-Smirnov test. Depending on whether the statistical hypotheses were fulfilled, either the Student's t-test or the Mann-Whitney U test was used to compare the independent continuous variables between the two groups, Wilcoxon signed rank test was used for intra-group evaluation of variables according to baseline such as PoF ve MMO. Statistical significance level was accepted as $p < 0.05$.

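### The only sentence defining the two groups sorts patients by treatment received, and nothing in the plan states analysis by randomised arm

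*Combined protocol and SAP*

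**What the plan says.** The Study Design section opens with "This is a two-armed, randomized, parallel interventional clinical study enrolling 36 patients". After the eligibility criteria, and just before the two techniques are described, comes the only definition of the groups: "Patients were grouped according to the treatment they received: Single Puncture Arthrocentesis as group SPA, Double Puncture Arthrocentesis as DPA".

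The Statistical Analysis section says that "either the Student's t-test or the Mann-Whitney U test was used to compare the independent continuous variables between the two groups". It does not say how those groups are formed. No part of the document names intention-to-treat, per-protocol, an analysis population or the allocated arm. Nor does it say how a converted or uncompleted procedure would be analysed.

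Two of the outcomes describe the procedure itself. For duration (item 4), "Total time for arthrocentesis was noted at the end of the procedure". For ease (item 5), "The operator rated the degree of easiness of the procedure on a VAS as 0-very easy 10-very difficult to perform".

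**The concern.** Randomisation protects a comparison of the arms as allocated. Regrouping by the procedure actually performed gives up that protection whenever the reason for switching is related to outcome. Taken literally, the group definition does this.

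A switch is physically conceivable, because the SPA needle enters at the first DPA reference point and a second needle could be added. That is inference; the document describes no such event. If joints that were hard to irrigate with one needle were switched to two, and those joints also had a worse prognosis, DPA would collect the poorer-prognosis patients and SPA would lose them. SPA would then look better with no true difference.

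For duration and ease, the literal rule would also credit the time and difficulty of a converted case to the technique finally used, not the one allocated.

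**Working it through.** **Text.** Set side by side, the Study Design section says the study is randomised, the group definition uses treatment received, and the Statistical Analysis section compares two groups that it does not redefine. The only definition available to the analysis is therefore the treatment-received one.

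**Inputs.** From the document: 36 patients in total and significance at 0.05. There is no power calculation to reproduce. Assumed for illustration:

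- 18 patients per arm, a two-sided pooled t-test, normal outcomes, SD 2 NRS points and no true effect.
- Each joint is difficult with probability k/18, so k per arm on average, for k = 1, 2, 3.
- Difficult joints score D points worse, for D = 2 or 3.

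**Shift under full one-way conversion.** Let K1 and K2 be the numbers of difficult joints in the SPA and DPA arms, each binomial(18, k/18). All K1 convert and no DPA joint does. As treated, SPA has 18 − K1 patients, none difficult, and DPA has 18 + K1 patients, of whom K1 + K2 are difficult. The expected shift (DPA minus SPA) is

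D × E[(K1 + K2)/(18 + K1)] = 0.103D, 0.197D, 0.282D for k = 1, 2, 3.

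As a rough check, replacing K1 and K2 by their mean k gives 2k/(18 + k) = 0.105, 0.200, 0.286.

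**Type I error** (200,000 simulated trials per case):

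| D | k | Shift (points) | As treated |
|---|---|---|---|
| 2 | 1 | 0.21 | 5.8% |
| 2 | 2 | 0.39 | 8.0% |
| 2 | 3 | 0.56 | 11.0% |
| 3 | 1 | 0.31 | 6.5% |
| 3 | 2 | 0.59 | 11.1% |
| 3 | 3 | 0.85 | 17.3% |

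The same trials analysed as randomised give a shift of 0 and an error of 4.9% to 5.1%.

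**Milder patterns.**

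- Half of the difficult SPA joints convert: shift 0.10 to 0.41, error 5.2% to 7.8%.
- All difficult SPA joints and one third of difficult DPA joints convert (k = 3): shift 0.38 and 0.56, error 7.4% and 9.6%, for D = 2 and 3.
- Full conversion both ways: shift 0, error 3.5% to 4.9%.
- One-way conversion unrelated to prognosis, or D = 0: shift 0, error 4.9% to 5.0%.

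**Sensitivity to SD.** Moving the SD from 1.5 to 3 under full one-way conversion takes the error from 10.0% to 6.5% for k = 2, D = 2, and from 23.8% to 11.2% for k = 3, D = 3. The last pair is the extreme corner of the range.

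**Scale.** With 18 per arm, 80% power needs a difference of about (1.960 + 0.842) × √(2/18) = 0.93 SD, or 1.87 points at SD 2. A shift of 0.39 is 0.39/1.87 = 21% of that.

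**Duration.** Suppose one SPA case converts and the conversion adds m = 5 to 15 minutes (assumed). As randomised, the added time raises the SPA mean by m/18 = 0.28 to 0.83 min. As treated, it raises the DPA mean by m/19 = 0.26 to 0.79 min. These figures count only the added minutes, not any difference in typical duration between the techniques.

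**The case against.** The strongest reply is that the sentence only labels the arms. It follows the statement that the study is randomised, it assigns abbreviations, and it sits before the technique descriptions and outside the Statistical Analysis section. With one procedure per patient, treatment received is common loose wording for treatment assigned. This is a plausible reading and it stands as such. It does not settle the matter, because no other sentence says who is analysed in which arm and the only relevant text points the other way.

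The second reply is that the document mentions no conversion, failed puncture or crossover. Harm needs several things together: conversions occurred, they were related to prognosis, they ran mainly one way, and the literal rule was applied. None is shown. This also stands, and it limits the point to a conditional one. The largest figures assume the most adverse conversion pattern considered.

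The third reply is that, for duration and ease, crediting the technique completed answers a legitimate but different question. That is fair. The plan should still say which question it asks, and the sums involved are under a minute per converted case.

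Finally, counting conversions requires that allocation and conversions were recorded, and the document does not describe those records.

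**Conclusion.** The concern holds as a minor one, with medium confidence. The wording is certain: the only group definition uses treatment received, and nothing restores the randomised arm. The bias is conditional. With no conversions, balanced conversions, or conversions unrelated to prognosis, the pain comparison is not biased. With prognosis-related conversion mainly one way, an average of 1 to 3 difficult joints per arm gives a shift between 0.10 and 0.85 points and a type I error between 5.2% and 17.3% at SD 2, from half to full conversion of the difficult SPA joints. Only the total of 36 and the 0.05 level come from the document; arm sizes, SD, difficulty rate, prognostic gap and conversion pattern are assumptions. This is an ambiguity to resolve, not a demonstrated bias.

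**What to change.** Replace the group definition with: *Patients are analysed in the arm to which they were randomised (SPA or DPA), whatever procedure was completed.* Report the number of converted or uncompleted procedures in each arm, stating zero if there were none. Keep any as-treated comparison, including for duration and ease, as a sensitivity analysis only.

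The cost is one sentence and one count per arm. The outcome data do not change, and the result is identical if no patient crossed over. If some did, the allocation list and the procedure records are needed to place them.

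### Does a measurement rule that names only masseter pain undermine the outcome called pain-free maximum mouth opening?

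*Combined protocol and SAP*

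**What the plan says.** All references are to the combined protocol and SAP.

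- **Outcome measures, item 2, name:** "The measurement of pain-free maximum mouth opening (MMO) in millimeters". The name does not limit the pain to any site.
- **Item 2, rule:** a caliper distance between upper and lower front teeth, with the mouth "open as possible without any assistance and without pain in masseter muscle". The sentence containing this rule has pain-free MMO as its subject. Of repeat readings it says: "Three measurements were performed, and their average is recorded".
- **Item 2, timing:** before the procedure, then at 1 week and at 1, 3 and 6 months.
- **Items 9 to 11:** the other jaw movements have no pain condition. Lateral movement is read while the "mandible was shifted towards the affected TMJ" (item 9) or away from it (item 10), and protrusion "by a caliper when mandible moves forward" (item 11).
- **Items 1 and 3:** pain on function and pain at rest are scored from 0 to 10 at the same five visits.
- **Statistical Analysis:** continuous variables are compared between groups by t-test or Mann-Whitney U test. MMO is one of two variables named as examples for the within-group Wilcoxon comparison with baseline.

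No other part of the document defines MMO further.

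**The concern.** The name promises an opening free of pain, while the rule excludes pain at one site, a chewing muscle. The disorder under study lies in the joint, and the treatment is lavage of the joint: in the double puncture technique the "upper joint cavity was irrigated with 200 mL" of solution. Joint pain is therefore a plausible limit to opening, and the rule is silent on it. In a patient with joint pain but no masseter pain, two assessors could stop at different points.

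MMO is not a peripheral measure. "Restricted mouth opening" is an inclusion criterion, and MMO is the only jaw-movement outcome with a pain condition. If the masseter-only rule was applied, a rise in MMO shows wider opening without masseter pain, and a reader who trusts the label might take it as wider opening without any pain. What is at stake is the meaning of the outcome, chiefly for change from baseline.

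**Working it through.** The plan gives no figure to reproduce, so the check sets the two readings side by side and asks what would differ between them.

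**Inputs.** The name and rule in item 2; the pain scores in items 1 and 3; the analyses in Statistical Analysis. The document gives no mean, standard deviation or expected difference for MMO, and no frequency of joint pain on opening.

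**Step 1: the two readings.** For one patient at one visit, let L be the widest unassisted opening, M the opening at which masseter pain begins and J the opening at which joint pain begins (M or J is unlimited if that pain does not occur). Take joint pain as the only other pain that matters.

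- Any-pain reading: A = min(L, M, J)
- Masseter-only reading: B = min(L, M)
- Gap: D = B − A = max(0, B − J), which is never negative

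D is zero whenever the opening is limited mechanically, or by masseter pain, before joint pain begins. Pain is not an inclusion criterion, so D could be zero for every patient.

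**Step 2: change from baseline.** (Change in B) − (change in A) = D after − D before. If the gap narrows after treatment, the masseter-only reading shows the smaller improvement, so the label would not flatter the treatment. If the gap widens, the opposite holds. The document does not say which to expect.

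**Step 3: between arms.** (Contrast in B) − (contrast in A) = mean D in the single puncture arm − mean D in the double puncture arm. This is zero if joint pain limits opening equally in both arms. If it does not, the two readings answer slightly different questions, but each is a proper randomised comparison of its own quantity, provided one rule was used throughout. The written rule does not vary by arm or visit. The document does not say who measured or whether they were blinded, so identical application cannot be confirmed. The supportable statement is that no between-arm bias is shown.

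**Step 4: can D be sized?** No. Neither J nor its frequency is given. Counting the MMO readings would not help, since the count would be the same for any remark about MMO.

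**Step 5: what could a change achieve?** The document is in the past tense. If the readings exist, they can be described or relabelled but not redefined; the visits, tests and sample of 36 stay as they are. Had measurement not begun, a rule to stop at the onset of any pain would choose between two meanings that the document leaves open. It would also have no defined endpoint in a patient who already has pain at rest, which item 3 allows for.

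**The case for a change.** The strongest case for a change is that the sentence is worded as the definition and names only the masseter. Nothing marks the muscle as an example. The pain scores cannot settle the matter, because neither records whether pain was present during the caliper reading. Clarification would cost one sentence.

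Much of this stands. The ambiguity is real, the rule actually applied cannot be recovered from the document, and a careful report will say which pain ended the opening. It is still an ambiguity and not a demonstrated measurement fault. The defining sentence carries the word pain-free itself, and the document's English is loose elsewhere, so an imprecise phrase is a plausible explanation, though not a proven one.

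Two supporting arguments carry little weight. Item 6 mentions "feeling of pressure in TMJ area and disturbing sound", but there it concerns how well patients tolerated adverse effects and complications, so it says nothing about where mouth opening was stopped. Items 9 to 11 make no claim to be pain-free, so their lack of a pain condition does not bear on item 2.

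**Conclusion.** No change to the plan is called for. The name and rule of item 2 do not match word for word, and it is unclear whether an opening reached with joint pain was recorded as pain-free. This is a gap in wording that the report can close by stating the rule used; if masseter pain alone ended the opening, the label should say so. Doing this changes no data, analysis or result.

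The size of any effect cannot be derived from the document and may be zero. The conclusion rests on two assumptions: that one rule was applied to both arms and at all visits, as the text implies, and that the readings have already been taken, as its tense suggests. If assessors had applied different rules in the two arms, that would be a fault of conduct, and the document gives no sign of it.

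### Outcome 6 rates how well complications are tolerated and no outcome records them as events, so equal tolerability scores are not evidence of equal safety

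*Combined protocol and SAP*

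**What the plan says.** Under Outcome measures, item 6 (treatment tolerability) is defined as "The degree to which overt adverse effects and post operative complications (pain, feeling of pressure in TMJ area and disturbing sound) can be tolerated"; the rater is the patient. The scale and timing follow: "Patients were asked to rate the tolerability on a 5 point scale as 0- lowest, 4-highest at operation day, 1st week, end of follow up" at the sixth month. One number therefore covers pain, pressure and sound together. The item does not ask whether an effect occurred, which one, or how severe it was, and it defines no rating for a patient who had none.

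Two other outcomes touch one of the three listed effects. Item 1 rates pain on function from 0 to 10. Item 3 does the same for pain at rest: "Patients rated their pain level at rest on a Numerical pain Scale". Both are taken before the operation, at week 1 and at months 1, 3 and 6.

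The other eight outcomes are mouth opening, procedure duration, ease for the operator, chewing efficiency, perceived effectiveness, two lateral movements and protrusion. There is no adverse-event section. The Statistical Analysis section describes variables by mean and standard deviation and names between-group tests for continuous variables only. It gives no summary or test for counts or proportions.

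The design is a "two-armed, randomized, parallel interventional clinical study enrolling 36 patients". In the technique descriptions, the single-puncture text adds "The joint was irrigated with 200 mL of RL solution under high pressure"; the double-puncture text gives the same volume and does not mention pressure.

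**The concern.** The trial compares two invasive techniques on the same joint, one with a single needle and one with two. A reader will want to know which of them produces more complications, and the plan itself names pressure and sound among the effects to be tolerated. The only measure that addresses this combines two things: whether an effect happened, and how the patient bore it. Arms with quite different complication frequencies could return similar scores, and those scores could then be read as showing similar safety.

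The month-6 rating is a further weak point. It comes long after the procedure, at the same visit as perceived effectiveness (item 8) and on the same 0-4 range. It may therefore partly reflect how well the treatment worked. That is an inference; the documents neither show it nor guard against it.

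**Working it through.** The documents give no complication rate and no sample-size derivation, so there is no stated figure to reproduce. The check is a reading of the text, followed by an illustration on assumed rates.

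**What is recorded for each listed effect**

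| Effect | Recorded as an event? | Recorded in another way? |
|---|---|---|
| Pain | No | 0-10 intensity at rest and on function, from week 1; not on operation day; procedural and disease pain not separated |
| Feeling of pressure | No | Only within the pooled 0-4 rating |
| Disturbing sound | No | Only within the pooled 0-4 rating |
| Any other complication | No | At most within the pooled 0-4 rating |

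**How far the score can move**

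Inputs: 36 patients (Study Design). The allocation ratio is not stated, so 18 per arm is assumed. Complications in 2 of 18 and 8 of 18 are also assumed, that is 2/18 = 11% and 8/18 = 44%. Unaffected patients are assumed to rate 4 and affected patients to average m.

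Arm mean = 4 − k(4 − m)/18, where k is the number affected. The difference between arms is (8 − 2)(4 − m)/18 = (4 − m)/3.

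| Average rating m of affected patients | Mean, k = 2 | Mean, k = 8 | Difference |
|---|---|---|---|
| 3.75 (three quarters rate 4, the rest 3) | 3.97 | 3.89 | 0.08 |
| 3.5 | 3.94 | 3.78 | 0.17 |
| 3 | 3.89 | 3.56 | 0.33 |
| 2 | 3.78 | 3.11 | 0.67 |

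The same 33-point difference in complication rate produces anything from 0.08 to 0.67 points on the scale. Neither m nor k can be recovered from the arm mean alone.

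**What recording events would give at this sample size**

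Fisher's exact test for 2/18 against 8/18 (10 events in 36 patients), lower tail:

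[C(18,0)·C(18,10) + C(18,1)·C(18,9) + C(18,2)·C(18,8)] / C(36,10) = (43,758 + 875,160 + 6,694,974) / 254,186,856 = 0.030.

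The arms are equal in size, so the two-sided p is 2 × 0.030 = 0.06. That is above the plan's 0.05 level (sidedness not stated; two-sided assumed).

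Exact 95% (Clopper-Pearson) intervals are 1.4% to 34.7% for 2/18 and 21.5% to 69.2% for 8/18.

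Power of Fisher's test with 18 per arm, by enumeration over all outcome pairs:

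- true rates 2/18 and 8/18: about 49%
- 10% against 30%: about 20%
- 10% against 50%: about 67%
- 10% against 60%: about 86%

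**The case against.** The strongest reply is that patient-rated tolerability is a legitimate construct, that operation day and week 1 are sensible times to ask about it, and that the plan makes no safety claim: its title concerns efficacy. All of that stands. The point is not that item 6 is a poor measure of acceptability, but that it cannot also serve as a record of complications.

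Three stronger readings are tempting, and the documents do not support them.

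- **That nothing else in the plan captures any complication.** Pain is rated 0-10 at rest and on function from week 1, with a preoperative baseline, so an excess of pain in one arm at week 1 could show there. What is missing is operation-day pain, attribution to the procedure, and everything other than pain.
- **That the score is blind to complications.** It falls in every row of the illustration. The defensible statement is that its sensitivity is unknown and depends on how patients rate. The 0.08 figure follows from one assumed rating pattern and should not be quoted without the range.
- **That recording events would let the trial detect a difference in safety.** With 36 patients it mostly would not: even 11% against 44% gives p = 0.06.

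The remark about pressure is also limited. The double-puncture text is silent on pressure, so the documents do not establish that it differed between the arms.

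**Conclusion.** The point holds in a narrow form. Followed as written, the plan cannot show how often pressure, disturbing sound or any other complication occurred in either arm, and it shows pain only as intensity from week 1. Equal tolerability scores would therefore not be evidence of equal safety, and unequal scores would not identify which complication differed or how often it occurred.

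This conclusion rests on the definition of item 6 and on the absence of any event record among the eleven outcomes. It does not depend on the assumed rates. The numerical illustration does depend on them, together with an 18:18 split, and it shows a mechanism rather than an estimate.

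Low power limits what the remedy can deliver but does not remove the need for it. Counts with wide intervals can still be read and combined with other studies; events that were never recorded cannot.

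**What to change.** - At operation day, week 1 and the later existing visits to month 6, record for each patient whether pain attributed to the procedure, feeling of pressure, disturbing sound or any other complication occurred (yes/no), with a severity for each.
- In the Statistical Analysis section, specify n (%) by arm for each complication and for any complication, with exact confidence intervals. State that this comparison is descriptive and that a non-significant difference is not evidence of equal safety.
- Keep the 0-4 rating as a separate acceptability outcome, and label the month-6 rating as recalled acceptability.
- If data collection is already complete, state in the report that complication incidence was not measured, and draw no safety conclusion from the tolerability scores.

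The cost is a slightly longer form at visits that already take place and one more table. No extra visits or patients are needed.

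### Lateral movement towards (LT) and away from (LA) the affected joint is recorded as an end-position midline gap with no closed-mouth reference, so any midline offset enters both outcomes and adds noise to the unadjusted comparison of the arms.

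*Combined protocol and SAP*

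**What the plan says.** All references are to the combined protocol and SAP.

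- **Outcome measures, item 9 (LT).** The title refers to movement of the mandible. The quantity recorded "was measured as the distance between the midlines of the upper and lower incisors by a caliper while patient's mandible was shifted towards the affected" side.
- **Outcome measures, item 10 (LA).** The rule is identical except for the direction: the reading is made "while patient's mandible was shifted away from the affected TMJ".
- **Replicates, both items.** "Three measurements were performed, and their average is recorded".
- **Visits, both items.** The timetable is the one used for most other outcomes: "Patients were evaluated at preoperatively and postoperatively 1st week, 1st month, 3rd month, 6th month".
- **Statistical Analysis.** For the arms, "either the Student's t-test or the Mann-Whitney U test was used to compare the independent continuous variables between the two groups". No change score or baseline adjustment is stated for this comparison. A Wilcoxon signed rank test against baseline is used within each group.
- **Eligibility.** The two exclusions are systemic disease affecting the joint and previous joint surgery. Neither concerns midline offset.

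The document names no closed-mouth or rest reading, reference mark, sign convention or correction for the midlines.

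**The concern.** A gap between the incisor midlines in the shifted position equals mandibular travel only if the midlines coincide when the teeth are closed. If the lower midline already sits to one side, the starting gap is counted as movement in one direction and taken off movement in the other. Averaging three readings reduces random reading error but leaves the offset, which is the same in all three.

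Two things are at stake. The first is meaning: a table of LT and LA in millimetres would be read as range of movement when it is not. The second is precision: in a trial of 36 patients, variation unrelated to technique goes straight into the standard error of the comparison between arms.

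**Working it through.** The plan gives no SD, power or target difference for LT or LA, so there is no figure of its own to reproduce.

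**Inputs.** From the document: 36 patients in two arms, a significance level of 0.05, and the definitions above. Assumed: 18 per arm, two-sided testing, SD of true travel *s* = 2 mm (range 1.5 to 2.5), SD of offset *t* = 0.5, 1.0 or 1.5 mm, and offset independent of travel.

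**Geometry.** Let *d* be the closed-mouth offset, positive towards the affected side. Then recorded LT = |true LT + *d*| and recorded LA = |true LA − *d*|. With true LT = LA = 7 mm:

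| *d* (mm) | LT recorded | LA recorded |
|---|---|---|
| 0 | 7 | 7 |
| 1 | 8 | 6 |
| 2 | 9 | 5 |

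**Change from baseline.** A stable offset cancels. With *d* = 2, true LT rising from 6 to 8 reads 8 to 10 (+2), and true LA rising from 4 to 7 reads 2 to 5 (+3); both changes are correct. There are two exceptions:

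- The offset itself changes. If *d* goes from 2 to 1 over the same visits, LT reads 8 to 9 (+1) and LA reads 2 to 6 (+4).
- The offset exceeds travel. With *d* = 2, true LA of 1 mm and of 3 mm both read 1 mm.

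**Bias between arms.** A simulation with no treatment effect (mean travel 7 mm, SD 2, offset SD 0, 1 or 2, 4,000 runs each) gave mean differences between arms of 0.01 mm or less in size and type I error of 4.6% to 5.1%. The comparison is unbiased.

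**Precision.** The variance ratio is (*s*² + *t*²)/*s*², and the effective total is 36 divided by that ratio. With 18 per arm, a two-sample t-test has 80% power at a standardised difference of 0.961. Dividing 0.961 by the square root of the ratio gives the power that remains.

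| *t* (mm), with *s* = 2 | Variance ratio | Effective total | Standardised difference | Power |
|---|---|---|---|---|
| 0 | 1.00 | 36 | 0.961 | 80% |
| 0.5 | 4.25/4 = 1.06 | 33.9 | 0.933 | 78% |
| 1.0 | 5/4 = 1.25 | 28.8 | 0.860 | 71% |
| 1.5 | 6.25/4 = 1.56 | 23.0 | 0.769 | 61% |

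Over the whole assumed grid the ratio runs from 1.04 (*s* = 2.5, *t* = 0.5) to 2.00 (*s* = 1.5, *t* = 1.5).

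**What can be done without an offset reading.** Let *r* be the correlation of true travel between baseline and follow-up, with equal SDs and a stable offset. The outcome variances are:

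- raw values: *s*² + *t*²
- change scores: 2(1 − *r*)*s*²
- ANCOVA: (*s*² + *t*²)(1 − ρ²), where ρ = (*rs*² + *t*²)/(*s*² + *t*²)

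For *s* = 2, *t* = 1:

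| *r* | Raw | Change | ρ | ANCOVA | ANCOVA if there were no offset, *s*²(1 − *r*²) |
|---|---|---|---|---|---|
| 0.3 | 5.00 | 5.60 | 2.2/5 = 0.44 | 4.03 | 3.64 |
| 0.5 | 5.00 | 4.00 | 3/5 = 0.60 | 3.20 | 3.00 |

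Change scores beat raw values only when *r* exceeds (1 − *t*²/*s*²)/2, which is 0.47, 0.38 and 0.22 for *t* = 0.5, 1.0 and 1.5. ANCOVA is below both in each row. Of the 1.00 mm² that the offset adds, ANCOVA leaves 0.39 at *r* = 0.3 and 0.20 at *r* = 0.5. It therefore absorbs most of a stable offset at moderate correlations, and less if *r* is very low.

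**The case against.** The strongest case against has four parts.

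- **No bias.** Offset is unrelated to the allocated technique, so randomisation protects the comparison. This stands. A reader might infer that chance imbalance in offset between the arms is a further harm. It is not: its standard error, *t*√(2/18), or 0.17 to 0.50 mm, is the same offset variance already counted in the test.
- **Within-patient change is largely safe.** A reader might infer that the Wilcoxon tests against baseline are also invalid. A stable offset cancels there, so this holds only where the offset changes or exceeds travel. The documents give no reason to think either is common.
- **The LT-LA contrast is not analysed.** The difference between LT and LA in one patient is wrong by 2*d*, and a reader might infer that a reported result is distorted by that amount. The plan states no test of LT against LA, so no planned result is affected in this way.
- **The size is unknown.** The documents give neither the spread nor the frequency of midline offset. If it is negligible in these patients, nothing is lost. The two outcomes are listed 9th and 10th of 11, and none is named as primary.

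What survives is that the stated rule does not measure what the outcomes are called, and the planned comparison of the arms does nothing to remove the resulting noise.

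**Conclusion.** The concern holds as a measurement-definition fault with a cost in precision. As written, LT and LA are midline gaps in the shifted position; they equal travel only in patients whose midlines coincide at closure. The comparison of the arms is valid but less precise than it need be. Under the assumptions of 18 per arm, travel SD 2 mm and two-sided 5% testing, a nominal 80% power becomes 78%, 71% or 61% for an offset SD of 0.5, 1.0 or 1.5 mm, with no loss at zero. The direction follows from the definition; the size rests wholly on assumed SDs. It is worth correcting because the remedy is cheap, but it does not threaten the trial's conclusions on its other outcomes.

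**What to change.** Rewrite items 9 and 10 so that LT and LA are the travel of the lower incisor midline from its closed-mouth position.

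- At each visit, record the closed-mouth midline offset with the same caliper, signed positive towards the affected joint. A single preoperative reading would assume that the offset never changes.
- Sign the end-position reading in the direction of the shift. Then LT = end position − offset, and LA = end position + offset.

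The document is written in the past tense, so the readings may already have been taken. If the offset was not recorded, compare the arms on LT and LA by ANCOVA with the preoperative reading as covariate, in preference to change scores, and describe raw LT and LA as midline gaps rather than movement. The fallback cannot repair readings where the offset changed or exceeded travel, and the report should say so.

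The cost is a few extra caliper readings per patient, with their small random error, and a sentence in each item. The fallback needs no new data and only a little more analysis work.
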